5. *Comparison intervention practitioner expertise.* Pragmatic trials do not standardize which and how practitioners implement the intervention. In this case, we will cluster-randomize all of the PCPs in our practice to the intervention and will not standardize who or how they will implement the communication strategies. Score = 5.
6. *Follow-up intensity.* Purely pragmatic trials do not have any formal follow-up visits of the individuals and use passive administrative databases to detect outcomes. Given the importance of patient-reported outcomes in this study, we will use a combination of passive and active follow-up methods to ascertain outcomes; these have low respondent burden and only require the completion of short questionnaires. Score = 4.
7. *Primary trial outcome.* Pragmatic trials select outcomes that are meaningful to study participants. Our main outcome will be pain interference, or how pain interferes with a patient's daily life, an outcome identified as meaningful by our patient partners. This outcome is important because while we seek to prevent inappropriate overuse of opioids, the flip side – discontinuing appropriate use of opioids – should also be prevented. The net outcome – pain interference – reflects a balance between inappropriate overuse and underuse of effective pain treatments. Score = 5.
8. *Participant compliance with "prescribed" intervention.* Pragmatic trials measure little or no patient "compliance" with the intervention. When we administer the questionnaires, we will ask whether individuals have received and read the PEAT materials via REDCap but we will not measure adherence to or use of PEATs. Score = 4.
9. *Practitioner adherence to study protocol.* Trials with pragmatic designs use unobtrusive or no methods to measure practitioner adherence to the study protocol. We will measure when and for whom the CDS alerts are activated, but will not report feedback to providers. Score = 4.
10. *Analysis of primary outcome.* PRECIS notes that pragmatic trials include all enrolled patients in the final analysis and there is no separation of the intention-to-treat (ITT) vs. per protocol (PP) patients. We will conduct both ITT and PP analyses for sensitivity analysis purposes. We will ask patients whether they received and read the PEAT materials and will examine when the CDS alerts were fired and for which patients to conduct a PP analysis. Score = 3.

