E4.e. Data Collection (RQ-2). Upon auto-enrollment, we will extract the following variables from the electronic health record: chronic pain condition, length of time with chronic pain diagnosis, race and ethnicity, language, marital status, history of pharmacologic treatment, surgical history related to chronic pain condition, past injuries related to chronic pain condition, and length of time with current primary care provider¹³⁷. When the intervention period is initiated, all eligible patients who have any follow-up visits during this 12-month period in both study arms will be sent the questionnaires. We will also capture depression scores via the Patient Health Questionnaires -PHQ-2 and/or PHQ-9 in the EHR. Furthermore, to determine if conversations about opioid medications took place during the visit that was

informed by either the CDS or the PEATS, we will conduct a structured review of a random sample of charts from both study arms.

E5. Statistical Analysis

E5.a. Descriptive and Exploratory Analyses. We will use frequencies and means for univariate descriptive analyses. We will use chi-square tests and paired t-tests to determine whether there are differences between the two study arms; using these bivariate analyses, we will identify covariates and patient- and physician-level moderators to use in the regression models. We will also consult with our Patient Partner to ensure that all appropriate patient-level covariates are included in the final models.

E5.b. Multi-Variate Regression Models. To evaluate the effectiveness of the comparators on the selected outcomes, we will use hierarchical linear regression models to measure changes in the outcomes over time using growth modeling statistical techniques¹³⁸ and will adjust for clustering at the patient, provider, and provider office level. Growth modeling allows the testing of individual differences in outcomes over time. In this study, we will examine HRQOL and communication scores over 12 months for the two study arms. We will adjust for patient- and provider-level covariates to account for potential confounders and also to identify whether there is heterogeneity of the treatment effect (see below). The proposed models are outlined here. We will test both fixed effects and random effects.¹³⁹ (IR-3):

Primary Outcome: Model 1: Hierarchical Linear Model (Longitudinal Analysis)

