Question: Which communication strategy used during the clinical encounter is more effective in reducing pain interference over time for patients with chronic pain who were taking opioids at baseline?

Dependent variable: Pain interference as measured by PROMIS Pain Interference Score (T-Score, Continuous)

Independent variable: Comparator received, CDS vs. PEAT (Dichotomous)

Potential Covariates: Age, gender, race, ethnicity, mental health comorbidities, chronic pain diagnosis, use of other pain medications (neuropathic pain medications, NSAIDS, antidepressants), benzodiazepine use, number of office visits during intervention period, baseline HRQOL, encounter month, physician years of practice, physician gender, employment, SES.

Moderator Analyses: We will use statistical interactions examining the moderating effects of patient age, race, ethnicity, mental health comorbidities, chronic pain diagnosis, physician years of practice and physician gender on the relationship between comparator and pain interference.

Mediation Analyses: We will test whether confidence in decision and satisfaction with communication as measured by COMRADE Scores mediates the relationship between the comparator used and the pain interference outcomes.

Primary Outcome: Model 2: Hierarchical Linear Model (Longitudinal Analysis)

Question: Which communication strategy used during the clinical encounter is more effective in improving how satisfied patients feel over time after communicating with their physician about chronic pain treatment risks and benefits?

Dependent variable: CG-CAHPS

Independent variable: Comparator received, CDS vs. PEAT (Dichotomous)

Potential Covariates: Age, gender, race, ethnicity, educational level, mental health comorbidities, chronic pain diagnosis, use of other prescribed pain medications (neuropathic pain medications, NSAIDS, antidepressants) benzodiazepine use, number of office visits during intervention period, baseline HRQOL, encounter month, physician years of practice, physician gender, employment, SES.

Subgroup Analyses: We will use statistical interactions examining the moderating effects of patient age, race, ethnicity, education level, mental health comorbidities, chronic pain diagnosis; and physician years of practice and gender on the relationship between comparator and pain interference.

Secondary Outcome: Model 3: Hierarchical Linear Model

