Question: Which communication strategy used during the clinical encounter is more effective in improving patient's Health Related Quality of Life over time?

Dependent variable: PROMIS Physical Function, PROMIS Depression, and PROMIS Pain Interference Scores (T-Scored, Continuous)

Independent variable: Comparator received, CDS vs. PEAT (Dichotomous). **Potential Covariates:** Same as Model 2.

Secondary Outcome: Model 4: Hierarchical Generalized Linear Model

Question: Which communication strategy used during the clinical encounter is more effective in reducing opioid prescriptions of more than 90 Morphine Milligram Equivalents (MME) over time?

Dependent variable: Opioid Prescription over 90MME (Dichotomous)

Independent variable: Comparator received, CDS vs. PEAT (Dichotomous). **Potential Covariates:** Same as Model 2.

Other Analyses: We will also perform a differences-in-differences analysis at the beginning and the end of the intervention to determine which strategy resulted in greater reduction in high-risk prescriptions.

Secondary Outcome: Model 5: Hierarchical Generalized Linear Model

Question: Which communication strategy used during the clinical encounter is more effective in reducing co-prescriptions of opioids and benzodiazepines over time?

Dependent variable: Opioids and Benzodiazepines Co-Prescribed (Dichotomous)

Independent variable: Comparator received, CDS vs. PEAT (Dichotomous). **Potential Covariates:** Same as Model 2.

Other Analyses: We will also perform a differences-in-differences analysis at the beginning and the end of the intervention to determine which strategy resulted in greater reduction in high-risk prescriptions.

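### Both primary models may adjust for visits made during the intervention, a post-randomisation variable, with covariates chosen by testing for arm differences

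*Combined protocol and SAP*

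**What the plan says.** Section E5.b gives each model a list of potential covariates. For Model 1 (PROMIS Pain Interference) and Model 2 (CG-CAHPS), both labelled primary, the list includes "number of office visits during intervention period". Models 3, 4 and 5 take their covariates as "Same as Model 2".

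Section E5.a describes how the final set is reached. It starts from arm comparisons: "We will use chi-square tests and paired t-tests to determine whether there are differences between the two study arms". It continues: "using these bivariate analyses, we will identify covariates and patient- and physician-level moderators to use in the regression models". A second route is consultation: "We will also consult with our Patient Partner to ensure that all appropriate patient-level covariates are included in the final models". The purpose given in E5.b is to deal with potential confounders and to look for heterogeneity.

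Nothing in E5.a or E5.b restricts covariates to baseline values or fixes a final list. The sensitivity analyses vary other things. Item 10 of the PRECIS list says "We will conduct both ITT and PP analyses for sensitivity analysis purposes", which changes the population. Section E7 (Missing Data) compares imputed with non-imputed data. Only Models 4 and 5 have an extra analysis with no listed covariates: "We will also perform a differences-in-differences analysis at the beginning and the end of the intervention".

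**The concern.** The Milestone Schedule (Attachment C-R) puts randomisation at 7/30/2017 and the start of the intervention at 1/1/2018. A visit count over the intervention period is therefore measured after randomisation and alongside the outcome. It cannot confound a randomised comparison. It can be a mediator (arm changes visits, visits change pain) or a collider (arm and follow-up pain both drive visits). Adjusting for a mediator removes part of the effect; adjusting for a collider can create an effect that does not exist.

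The selection rule makes this worse. If the visit count is among the variables tested, it is most likely to be selected when arm has changed it, and that is when adjusting does harm. It also means the primary model is not fixed before the data are seen.

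The plan's rationale for Aim 1 links patient activation with utilisation. That is an association and does not show that either arm changes visits, but it means an unchanged visit rate cannot simply be taken for granted.

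**Working it through.** **What can be checked.** The plan states no figure for this point, so there is none to reproduce. From the documents: planned difference 0.3 SD, alpha 0.05, ICC 0.02 and 320 patients per arm (E5.c), and 80 PCPs (E4.d). This gives 640 / 80 = 8 patients per PCP and 40 PCPs per arm. Everything about visits below is assumed.

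**Why the estimate moves.** In least squares,

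adjusted arm effect = unadjusted arm effect − b × d,

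where b is the coefficient of visits given arm and baseline, and d is the arm difference in visits given baseline. With no true effect, the shift is −b × d. It is zero if arm does not change visits (d = 0) or if visits carry no information on the outcome beyond arm and baseline (b = 0). If sicker patients visit more (b > 0), the arm with more visits looks better than it is.

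**Simulation, no true effect.** Each cell gives two values, for s = 0.3 / 0.5, meaning that visits rise exp(0.3) = 1.35 or exp(0.5) = 1.65 fold per SD of follow-up pain (or satisfaction).

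- *Single endpoint, OLS:* y = 0.6 × baseline + 0.8 × noise; visits ~ Poisson(exp(0.8 + ln(ratio) × arm + s × y)). Shifts use n = 2,000,000. False-positive rates use 320 per arm and 4,000 runs, adjusting for visits only when an arm t-test gives p < 0.05 (an assumed threshold; E5.a states none).
- *Growth model, arm main effect:* 12 complete monthly scores, 0.6 × baseline, intercept SD 0.6, slope SD 0.4, residual SD 0.51, PCP variance 0.02. Shifts use n = 800,000. Rates use 40 PCPs × 8 patients per arm, 3,000 runs and the same selection rule.
- *Model 2:* one score per visit (E9 sends CG-CAHPS after each visit), patient SD 0.7, residual SD 0.714, s of either sign. The absolute shift is shown.

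| Visit ratio | OLS shift, SD | Visits selected, % | OLS false positives, % | Growth shift, SD | Growth false positives, % | Model 2 shift, SD |
|---|---|---|---|---|---|---|
| 1.00 | 0 / 0 | 5.6 / 5.1 | 5.3 / 4.4 | 0 / 0 | 5.2 / 4.4 | 0 / 0 |
| 1.05 | −0.019 / −0.029 | 13.3 / 11.5 | 4.8 / 4.8 | −0.011 / −0.019 | 5.5 / 5.2 | 0.018 / 0.022 |
| 1.11 | −0.043 / −0.057 | 46.9 / 37.6 | 8.0 / 9.8 | −0.029 / −0.042 | 6.0 / 6.5 | 0.033 / 0.046 |
| 1.20 | −0.076 / −0.103 | 90.8 / 81.5 | 23.8 / 40.9 | −0.051 / −0.074 | 12.9 / 26.1 | 0.059 / 0.085 |
| 1.35 | −0.134 / −0.178 | 100 / 99.9 | 60.0 / 89.7 | −0.087 / −0.130 | 34.1 / 67.6 | 0.099 / 0.139 |

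With the visit covariate left out, the growth model's false-positive rate stays at 4.4 to 5.8%, and the Model 2 shift is at most 0.019 SD.

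**Relative to the planned effect.** At a ratio of 1.20, the Model 1 shift runs from 0.051 / 0.3 = 17% (growth) to 0.103 / 0.3 = 34% (OLS) of the design difference.

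**A second mechanism.** Here an unmeasured severity worth 0.5 SD on the outcome drives visits (80 physicians × 8 patients, about 3 visits each with a minimum of 1, cluster-robust errors, 500 runs). A ratio of 1.2 shifts the adjusted estimate by −0.07 to −0.08 SD, with rejection at 17 to 18%. A ratio of 1.4 shifts it by −0.14 to −0.16 SD, with rejection at 40 to 50%. Unadjusted rejection is 6 to 7%.

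**Real effects can be diluted.** In the growth model with a true −0.30 SD and no direct arm effect on visits, the estimate averages −0.288 / −0.257 SD after selection. If arm raises visits 1.4 fold, severity does not affect visits and each visit lowers the outcome by 0.05 SD, the unadjusted effect is about −0.06 SD and the adjusted one about 0.

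**Where there is no bias.** If visits depend on arm and baseline pain only, with baseline adjusted for, the OLS shift stays within 0.004 SD of zero for ratios from 1.05 to 1.35. In the growth model, the arm-by-time test keeps a false-positive rate of 4.4 to 5.6% when visits enter only as a main effect.

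**The case against.** The plan does not commit to this adjustment. The covariates are only potential ones, and E5.a neither names the visit count among the tested variables nor gives a threshold. The documents contain no evidence that either arm changes visit frequency: PEAT material goes out ahead of an existing visit (E4.c), and CDS alerts fire when an order is entered. E5.b speaks of change over time, which suggests an arm-by-time test, and that test is unaffected when visits enter only as a main effect. Baseline HRQOL is a listed covariate, so if visits follow baseline pain alone the bias disappears. The largest false-positive rates come from a single-endpoint model that is not the planned one. E6 also promises a Bonferroni correction.

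Most of this is right, and it limits the size of the problem. It does not remove it. E5.a and E5.b never say which term is tested. Nothing excludes the visit count from selection. Visits that track follow-up pain beyond baseline are at least as plausible as visits that do not. The reach of the Bonferroni sentence is unclear, since it sits in the subgroup section. At an assumed alpha of 0.025, the OLS false-positive rates are still about 16 to 32% at a ratio of 1.20 and 47 to 84% at 1.35. A smaller alpha does not correct a shifted estimate.

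**Conclusion.** The concern holds. Following the plan as written permits both primary models to adjust for a variable that the intervention may have altered, and the selection rule favours doing so when it has. No analysis named for Models 1 to 3 would expose the distortion.

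Whether it would occur, how large it would be and which arm it would favour cannot be settled from the documents. Harm to Model 1 requires three things: an arm effect on visits, visits that track follow-up pain beyond baseline, and a test of the arm main effect (or a visit term that interacts with time). Under the assumed inputs, clear harm begins at an arm difference in visits of about 20%. The point should be corrected before analysis, but it does not undermine the design.

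Two related weaknesses do not affect this conclusion. The arms contain different patients, so a paired t-test is not the right comparison. The timing of benzodiazepine use as a covariate is not stated, although concurrent use forms part of the Model 5 outcome.

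**What to change.** - Prespecify one covariate set for Models 1 to 5, all measured before the intervention starts, and delete selection by arm-difference tests. Patient Partner advice can shape that list before data are seen.
- Remove the intervention-period visit count from the main models, or replace it with a prior-year count from the EHR visit records used for the eligibility check in D2. Use the intervention-period count and follow-up medications only in a labelled secondary or mediation analysis.
- Take benzodiazepine and other pain-medication covariates at pre-intervention values; E4.e already extracts medication history at enrolment.
- Describe arm comparisons with unpaired methods that allow for clustering.

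The cost is wording, plus one EHR extraction if the prior-year count is used: D2 needs only a check for at least two visits, and the E4.e extraction list has no visit count. A little precision may be lost. No stated sample size, alpha or power changes.

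This does not deal with the separate exclusion of patients who have no visit in the intervention period (D2 and E7), which needs its own treatment. In the OLS setup above, that exclusion without the visit covariate shifts Model 1 by at most about 0.03 SD.

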E4.d. Recruitment Procedures (PC-2). Patients meeting inclusion criteria who are managed by one of the 80 participating PCPs at the Cedars-Sinai Medical Network will be auto-enrolled in the study. Patients will receive a written notification via mail of their inclusion in the study and at that time they will be told about the study details, including research procedures and requirements for follow-up, as well as the risks and benefits of study participation. At this time, patients will have the opportunity to actively opt out of receiving the education materials (if they are randomized to PEAT arm). Patients who do not opt out will receive education materials and their care will proceed as usual. Patients who are passively enrolled will receive the study questionnaires via REDCap. We estimate that out of the 4,000 patients eligible for the study (calculated from a quality improvement project based on claims data), approximately 30% will complete all of the questionnaires, which is in line with our sample size calculations. Once the patients complete monthly questionnaires, we will provide a \$5 gift card for filling out the enrollment survey. We have budgeted \$25 per patient as

a financial incentive for completing the questionnaires (Appendix I, **Table 1 for Recruitment Plan** and **Table 2 for Passive Enrollment Estimates**).

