E5.c. Power Calculations. Guided by previous work in chronic pain interventions,¹⁴⁰ we calculated sample size using an intracluster correlation coefficient of 0.02, an α level of 0.05, 90% power, and detection of a mean (SD) difference of 0.3 standard deviations on the PROMIS Pain Interference scale. We calculated a sample size of 320 patients per study arm, for a total of 640 patients. To compensate for predicted loss to follow-up, multiple variables in the final multi-level models, as well as sub-group analyses, we inflated the sample size by 50% to 960. Since we will be examining the effect of the interventions on a variety of sub-groups within the study sample, such as diagnoses of mental health conditions, race, ethnicity, gender, and chronic pain diagnosis, we will be adequately powered to detect meaningful differences. In our original proposal, we calculated a sample size of 320 patients per study arm for a total of 640 patients. To compensate for predicted loss to follow-up and non-response we had inflated the recruitment target size by 50% to 960. Under the current modification – and given the absence of changes to the assessment schedule, the estimated intracluster correlation coefficient, and the expected mean difference - the sample size required to adequately power the analysis remains unchanged. We believe the recruitment target will also remain consistent, and potentially even fall due to the ability of study staff to call passively enrolled patients and remind them to respond to assessments. We therefore anticipate being adequately powered to detect meaningful differences between the two arms.

E6 Heterogeneity of Treatment Effect (HT-1, HT-3, HT-4)

After reviewing the literature and consulting with our patient partners, we identified specific subgroups we plan to analyze to identify whether there is a heterogeneity of the treatment effects. Below we detail our planned sub-group analyses, our hypotheses, and our plans for statistical analysis for each subgroup. In order to address the problem of multiplicity, a Bonferroni correction will apply to all analyses.

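### Models 4 and 5 inherit a covariate list that does not name the pre-intervention value of the prescribing outcome, although those data are already being collected

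*Combined protocol and SAP*

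**What the plan says.** Section E5.b defines two hierarchical generalized linear models for Aim 3. Model 4 has "Dependent variable: Opioid Prescription over 90MME (Dichotomous"; Model 5 has a yes/no indicator of opioid-benzodiazepine co-prescription. Both refer back to Model 2, the CG-CAHPS model, for their potential covariates. That list ends with "baseline HRQOL, encounter month, physician years of practice, physician gender, employment, SES". It also contains use of other pain medications (non-opioid classes only) and benzodiazepine use, with no date attached. It does not contain baseline status above 90 MME, baseline co-prescription, opioid dose or duration of opioid use.

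Under Other Analyses, each prescribing model adds: "We will also perform a differences-in-differences analysis at the beginning and the end of the intervention".

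The raw material for a baseline term is planned. Section E4.e extracts "history of pharmacologic treatment" at auto-enrolment, the EHR and pharmaceutical claims section (item 4 under Outcome Measurement) collects opioid prescriptions, and the Milestone Schedule starts pharmacy pulls on 8/1/2017, with the intervention starting on 1/1/2018.

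Section E5.a says covariates will be identified from bivariate comparisons between the arms and in consultation with the Patient Partner.

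**The concern.** A covariate list built for a patient-experience score was carried over to prescribing outcomes, so the one baseline score it names belongs to a different outcome. A patient's earlier prescribing status is likely to be among the best predictors of later status, and D1 deliberately mixes recent starters with longer-term users. PCPs are assigned with a random number generator, and no stratification on prescribing is described, so the arms may differ by chance in their share of high-dose patients.

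The selection rule in E5.a does not close the gap. A test between arms detects imbalance, not prognostic strength, so it could pass over a strong predictor that happens to be balanced.

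Model 5 has a further difficulty. If benzodiazepine use is measured during follow-up, it is a component of the outcome and should not be a covariate.

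At stake is power for the Aim 3 comparison, and clarity about which of two analyses with different precision carries its conclusion.

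**Working it through.** **The plan's own figure.** The only sample-size calculation (E5.c) is for pain interference: "detection of a mean (SD) difference of 0.3 standard deviations on the PROMIS Pain Interference scale", "an α level of 0.05, 90% power" and "an intracluster correlation coefficient of 0.02", giving 320 per arm. With a two-sided test (assumed), the individually randomized size is 234 per arm. With 640 patients over the 80 PCPs (E4.d), there are 8 per PCP, the design effect is 1 + 7 × 0.02 = 1.14, and the result is 267 per arm. The figure of 320 needs an unstated cluster size of about 18 to 20. That is a separate matter. No power or sample size is given for Models 4 and 5, nor any prevalence or baseline-to-follow-up correlation, so everything below is a range under assumptions.

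**Step 1: linear approximation.** Let r be the correlation between baseline and follow-up, with equal variances at both times. Relative to a follow-up-only analysis (variance 1), difference-in-differences has variance 2(1 − r) and baseline adjustment has 1 − r². The ratio of adjusted to difference-in-differences is (1 + r)/2.

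| r (assumed) | Adjusted | Diff-in-diff | Adjusted vs follow-up-only | Adjusted vs diff-in-diff |
|---|---|---|---|---|
| 0.3 | 0.91 | 1.40 | 9% lower | 35% lower |
| 0.5 | 0.75 | 1.00 | 25% lower | 25% lower |
| 0.7 | 0.51 | 0.60 | 49% lower | 15% lower |

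Below r = 0.5, difference-in-differences is less precise than ignoring baseline altogether.

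**Step 2: simulation with clustering.** Assumptions: 640 patients, 80 clusters, ICC 0.02 on a latent scale, baseline rate 20%, follow-up rates 20% and 12%, linear-probability models with cluster-robust standard errors, 600 runs. Here phi is the correlation between the two binary values.

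| phi | Power, follow-up-only | Power, adjusted | Power, diff-in-diff |
|---|---|---|---|
| 0.35 | 79% | 84% | 65% |
| 0.53 | 77% | 92% | 80% |
| 0.73 | 77% | 98% | 95% |

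**Step 3: logistic scale.** Models 4 and 5 are generalized linear models for binary outcomes, where the variance formulas do not carry over directly. In a simulation without clustering (1,200 patients, 10% prevalence, conditional log odds ratio of magnitude 0.7), adding baseline status raised the standard error of the log odds ratio from 0.221 to 0.253 at phi 0.5, and from 0.211 to 0.295 at phi 0.7. Power still rose, from 69% to 80% and from 47% to 71%, because the adjusted estimate lies further from zero. The adjusted odds ratio is conditional on baseline and is a different quantity from the unadjusted one.

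**Step 4: which sample size applies.** Take 10% prevalence (assumed), 80% power, ICC 0.02, and detectable difference = 2.80 × √(2 × 0.09 × variance ratio / effective n per arm).

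- Expected questionnaire completers: 30% of 4,000 = 1,200, or 15 per PCP. Effective n = 600/1.28 = 469, giving 5.5 points without adjustment.
- All eligible patients: 4,000, or 50 per PCP. Effective n = 2,000/1.98 = 1,010, giving 3.7 points without adjustment, and 3.7 × √0.75 = 3.2 points at r = 0.5.

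Prescribing outcomes come from the EHR and claims and need no completed questionnaire, so the second case is the closer one if all eligible patients are analysed.

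**The case against.** The strongest reply is that baseline is not ignored. The difference-in-differences uses the starting value and removes chance imbalance in it, and Aim 3 asks about reduction, which a change contrast addresses directly. E5.b also describes growth models with a patient level, and the questions for Models 4 and 5 concern change over time; a pre-intervention record in the outcome series would bring baseline into the model. Benzodiazepine use is listed, and since patients are selected on opioid prescriptions, a baseline measurement of it would come close to baseline co-prescription. The lists are headed as potential covariates, so nothing is formally excluded.

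Much of this stands. A reader might infer that the plan discards baseline prescribing, or that chance imbalance stays in every Aim 3 result. The difference-in-differences contradicts both. A reader might also put the loss at the equivalent of 33% to 96% more patients (1/0.75 and 1/0.51). That is a linear-model result, against a wholly unadjusted follow-up-only analysis, at an assumed r of 0.5 to 0.7; the plan lists many other covariates and a change analysis. Nor do the documents support saying that the logistic standard error would shrink.

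What does not stand is that the matter is therefore settled. The difference-in-differences sits under Other Analyses and runs from the beginning of the intervention with no fixed pre-intervention window. Models 1 and 2 are labelled longitudinal, whereas 4 and 5 are not. The sentence on 12 months of scores names HRQOL and communication only, and the mental-health subgroup in E6 refers to high-risk prescriptions at the end of the intervention. Whether a pre-intervention record enters Models 4 and 5 is left open.

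**Conclusion.** The point holds as a failure to pre-specify. The covariate list for Models 4 and 5 does not name the pre-intervention value of the outcome, the main-model text does not otherwise say that it is used, and the data for it are already planned. Because PCPs are randomized, this concerns efficiency and clarity, not systematic bias, and it affects secondary outcomes only.

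The size rests on r, which the documents do not give. Against follow-up-only, the gain runs from slight (r = 0.3) to large (r = 0.7); against the planned difference-in-differences it runs the other way, largest at low r. Under every correlation examined, the baseline-adjusted analysis had the highest power of the three. The undated benzodiazepine covariate in Model 5 needs correcting whatever r is.

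A reader might extend the argument to Models 1 to 3, whose lists also omit opioid dose and duration. Those models already list baseline HRQOL, and nothing in the documents shows what dose or duration would add, so that extension is optional and unquantified.

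**What to change.** Amend E5.b as follows.

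1. Define one fixed window before the intervention starts on 1/1/2018, the same for both arms, from which all baseline prescribing terms are taken. As the Milestone Schedule lets enrolment run to 12/31/2018, state how patients with no opioid record in that window are coded.
2. In Model 4, pre-specify baseline status above 90 MME as a covariate, with baseline MME as an option.
3. In Model 5, pre-specify baseline opioid-benzodiazepine co-prescription, and let it replace the undated benzodiazepine use.
4. Include these terms whatever the between-arm tests in E5.a show.
5. Name the baseline-adjusted model as the main Aim 3 analysis and keep difference-in-differences as a sensitivity analysis. State that the odds ratio is conditional on baseline.
6. State whether the outcome series in Models 4 and 5 contains a pre-intervention record. If it does, say how that record and the baseline covariate are handled, so that the same value is not used both as outcome and as covariate.

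The cost is SAP wording and a derived variable for each model. No new data collection is needed, since the pharmacy pulls are scheduled to begin five months before the intervention.
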